6.2 IMPORTANT PROTOCOL VIOLATIONS

Data discrepancies and deviations from the CTP will be identified for all subjects in the database (i.e., treated subjects and subjects with serious AE (SAE) which the investigator considered related to the screening procedure). Consistency check listings (for identification of violations of time windows) and a list of protocol deviations (e.g. deviations in drug administration, in blood sampling times, etc.) will be provided to be discussed at the report planning meeting (RPM) and data base lock meeting (RPM/DBL). At this meeting, it will be decided whether a discrepant data value can be used in analyses or whether it must be corrected in the clinical database.

Each protocol deviation must be assessed to determine whether it is an important protocol violation (PV). For definition of important PVs, and for the process of identification of these, refer to the Boehringer Ingelheim reference document 'Protocol Violation Handling Definitions' [\(2\)](#).

If any important PVs are identified, they are to be summarised into categories and will be captured in the RPM minutes via accompanying Excel spreadsheet [\(3\)](#). The following table contains the categories which are considered to be important PVs in this trial. If the data show other important PVs, this table will be supplemented accordingly by the time of the RPM. If substantial numbers of PVs are reported at the RPM, a decision about summarising the PVs in a tabular format will be made. Otherwise, only a PV listing will be provided.

The following [Table 6.2: 1](#) gives the important PVs for this trial.

Table 6.2: 1 Important Protocol violations

Category	Description
/ Code	
A Entrance criteria not met	
A1	Inclusion criteria violated
A2	Exclusion criteria violated
B Informed consent	
B1	Informed consent not available
B2	Informed consent too late
C Trial medication and randomization	
C1	Incorrect trial medication taken
C2	Non-compliance
C3	Incorrect intake of trial medication
D Concomitant medication	
D1	Prohibited medication use
E Missing data	
E1	Certain violations of procedures used to measure primary or secondary data
F Incorrect timing	
F1	Certain violations of time schedule used to measure primary or secondary data.
G Other trial specific important violations	
G1	Incorrect intake of meal

6.3 SUBJECT SETS ANALYSED

- **Entered set (ES):**

This subject set includes all entered subjects, whether treated or not.

- **Treated set (TS):**

This subject set includes all subjects from the ES who were dispensed study medication and were documented to have taken at least one dose of investigational treatment.

This is the full analysis set population in the sense of ICH-E9 [\(1\)](#). It is used for safety analysis.

Section 7.3.1 of the CTP:

Primary and secondary pharmacokinetic parameters of a subject will be included in the statistical pharmacokinetic (PK) analyses if they are not flagged for exclusion due to a protocol violation relevant to the evaluation of PK (to be decided no later than in the Report Planning Meeting) or due to PK non-evaluability (as revealed during data analysis, based on the criteria specified below). Exclusion of a subject's data will be documented in the CTR.

Relevant protocol violations may be

- *Incorrect trial medication taken, i.e. the subject received at least one dose of trial medication the subject was not assigned to*
- *Incorrect dose of trial medication taken*
- *Use of restricted medications.*

Plasma concentrations and/or parameters of a subject will be considered as non-evaluable, if for example

- *the subject experienced emesis that occurred at or before two times median t_{max} of the respective treatment (Median t_{max} is to be determined excluding the subjects experiencing emesis),*
- *a pre-dose concentration is >5% of the C_{max} value of that subject*
- *missing samples/concentration data at important phases of PK disposition curve.*

- **Pharmacokinetic set (PKS):**

The PK parameter analysis set (PKS) includes all subjects in the TS who provide at least one primary or secondary PK parameter that was not excluded according to the description above. Thus, a subject will be included in the PKS, even if she contributes

only one PK parameter value for one period to the statistical assessment. It is used for the PK analysis.

The discussion of all exceptional cases and problems and the decisions on the allocation of subjects to populations will be made at latest at the RPM.

The following table summarizes which subject sets will be used for the different analyses.

Table 6.3: 1 Subject sets analysed

Class of endpoint	ES	TS	PKS
Disposition, exposure	X		
Important PVs	X		
Primary endpoints			X
Secondary endpoints and further parameters of interest in PK analyses			X
Safety endpoints		X	
Demographic/baseline endpoints		X	

6.5 POOLING OF CENTRES

This section is not applicable, because the study was performed in only one centre.

6.6 HANDLING OF MISSING DATA AND OUTLIERS

Handling of missing data will be according to the CTP, Section 7.4. Additionally, handling information of missing data is shown as follows:

- Missing data and outliers of PK data are handled according to [\(4\)](#).
- Missing or incomplete AE dates are imputed according to BI standards (see “Handling of missing and incomplete AE dates”) [\(5\)](#).

6.7 BASELINE, TIME WINDOWS AND CALCULATED VISITS

The baseline values of laboratory data and value of vital sign for safety analysis will be defined as the last values before first drug administration.

Time windows are defined in Section 6.1 of the CTP. Adherence to time windows will be checked at the RPM/DBLM.

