## FLOW CHART

Period	Visit	Day	Planned time (relative to drug administration [h:min]	Approximate clock time of actual day [h:min]	Event and comment	Safety laboratory	PK blood for EE and LNG	PK blood for BI 409306	12-lead ECG	Pregnancy test	Vital signs (BP, PR)	Questioning for AEs and concomitant therapy 
SCR	1	-70 to -29			Screening (SCR) 	x 				x	x	
Run-in 	2	-49 to -8			Microgynon® intake 							x 
		-3 to -1			Ambulatory visit	x			x	x	x	x
Treatment	3	1	-02:00	07:00								x
			00:00	09:00	Drug administration (ambulatory): Microgynon®	x 						x
		2	24:00	09:00	Drug administration (ambulatory): Microgynon®							x
		3	48:00	09:00	Drug administration (ambulatory): Microgynon®							x
		4	72:00	09:00	Drug administration (ambulatory): Microgynon®							x
		5	96:00	09:00	Drug administration (ambulatory): Microgynon®							x
		6	120:00	09:00	Drug administration (ambulatory): Microgynon®							x
		7	144:00	09:00	Drug administration (ambulatory): Microgynon®							x
		8	168:00	09:00	Drug administration (ambulatory): Microgynon®							x
		9	192:00	09:00	Drug administration (ambulatory): Microgynon®							x
		10	216:00	09:00	Drug administration (ambulatory): Microgynon®							x
		11	240:00	09:00	Drug administration (ambulatory): Microgynon®							x
		12	264:00	09:00	Drug administration (ambulatory): Microgynon®							x
		13	288:00	09:00	Drug administration (ambulatory): Microgynon®							x
		14	312:00	09:00	Drug administration (ambulatory): Microgynon®							x
		15	336:00	09:00	Drug administration (ambulatory): Microgynon®							x

Proprietary confidential information © 2017 Boehringer Ingelheim International GmbH or one or more of its affiliated companies

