### **5.2.3 Assessment of safety laboratory parameters**

For the assessment of laboratory parameters, blood and urine samples will be collected by the trial site at the time points indicated in the [Flow Chart](#) after the subjects have fasted for at least 10 h. Overnight fasting is not required at the discretion of the investigator or designate for retests.

The parameters that will be determined are listed in [Tables 5.2.3: 1](#) and [5.2.3: 2](#). Reference ranges will be provided in the ISF.

Manual differential white blood cell count or urine sediment examinations will only be performed if there is a clinically relevant abnormality in the automatic blood cell count or in the urinalysis, respectively.

Proprietary confidential information © 2017 Boehringer Ingelheim International GmbH or one or more of its affiliated companies

**Table 5.2.3: 1** Routine laboratory tests

Functional lab group	Test name	Set A 	Set B 	Set C 
Hematology	Hematocrit	x	x	x
	Hemoglobin	x	x	x
	Red blood cell count (RBC)	x	x	x
	Reticulocyte count	x	-	-
	White blood cell count (WBC)	x	x	x
	Platelet count	x	x	x
Automatic WBC differential (relative)	Neutrophils, eosinophils, basophils, monocytes, lymphocytes	x	x	x
Manual differential WBC (if automatic differential WBC is clinically relevant abnormal)	Polymorphnuclear neutrophils (segs), band neutrophils (stabs), eosinophils, basophils, monocytes, lymphocytes	x	x	x
Coagulation	Activated partial thromboplastin time (aPTT)	x	-	x
	Prothrombin time (Quick's test and INR)	x	-	x
	Thrombophilic tests 	x	-	-
Enzymes	Aspartate transaminase (AST/GOT)	x	x	x
	Alanine transaminase (ALT/GPT)	x	x	x
	Alkaline phosphatase (ALP)	x	x	x
	Gamma-glutamyl transferase (GGT)	x	x	x
	Creatine kinase (CK)	x	x	x
	CK-MB, only if CK is elevated	x	x	x
	Lactate dehydrogenase (LDH)	x	x	x
	Amylase	x	-	-
	Lipase	x	-	-
Hormones	Thyroid stimulating hormone (TSH)	x	-	-
Substrates	Serum Glucose	x	x	x
	Creatinine	x	x	x
	Total bilirubin	x	x	x
	Direct bilirubin	x	x	x
	Total protein	x	-	-
	Uric acid	x	-	-
	Total cholesterol	x	-	-
	Triglycerides	x	-	-
	hs-CRP (high sensitivity C-Reactive Protein)	x	x	x

 Parameters of Set A will be determined at the screening examination

 Parameters of Set B will be determined during treatment periods at the time points given in the [Flow Chart](#)

 Parameters of Set C will be determined at the end of trial examination

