### **7.3.3 Safety analyses**

Safety will be assessed for the endpoints listed in [Section 5.2.1](#). All treated subjects (that is, all subjects who received at least one dose of study drug), will be included in the safety evaluation. Safety analyses will be descriptive in nature and will be based on BI standards.

The analyses will be done by 'treatment at onset'.

Treatments will be compared in a descriptive way. Tabulations of frequencies/proportions will be used for the evaluation of categorical (qualitative) data, and tabulations of descriptive statistics will be used to analyse continuous (quantitative) data.

Measurements (such as ECG, vital signs, or laboratory parameters) or AEs will be assigned to treatments (see [Section 4.1](#)) based on the actual treatment at the planned time of the measurement or on the recorded time of AE onset (concept of treatment emergent AEs).

Therefore, measurements planned or AEs recorded prior to first intake of trial medication will be assigned to 'screening', those between first trial medication intake until end of the residual effect period (see [5.2.2.2](#)) will be assigned to the treatment period. Events after the residual effect period but prior to end of trial examination will be summarized as 'follow-up'. These assignments including the corresponding time intervals will be defined in detail in the TSAP.

Adverse events will be coded using the Medical Dictionary for Regulatory Activities (MedDRA). Frequency, intensity and causal relationship of AEs will be tabulated by treatment, primary system organ class and preferred term. SAEs and other significant AEs (according to ICH E3), and AESIs will be listed separately (see [Section 5.2.2.1](#)).

Laboratory data will be compared to their reference ranges. Values outside the reference range will be flagged. Additionally, differences from baseline (Day 1 of period 1) will be evaluated.

For vital signs, the differences from baseline will be evaluated.

Relevant ECG findings will be reported as AEs.

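### Does the SAP's laboratory baseline (last value before first drug administration) conflict harmfully with the protocol's Day 1 baseline?

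*SAP*

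**What the plan says.** Protocol 7.3.3 compares laboratory values with their reference ranges and adds that "differences from baseline (Day 1 of period 1) will be evaluated". For the other measurements it names no day: "For vital signs, the differences from baseline will be evaluated".

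SAP 6.7 gives one rule for both: "The baseline values of laboratory data and value of vital sign for safety analysis will be defined as the last values before first drug administration". It does not say whether that drug is the first run-in Microgynon tablet, the Day 1 Microgynon tablet or the first BI 409306 tablet. SAP Section 4 states that the planned analysis is unchanged, and SAP 7.8 refers back to the protocol for the safety analysis. SAP 7.8.2 plans summaries of baseline, on-treatment values and changes, plus counts inside and outside the reference range at baseline and at the last on-treatment measurement.

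Which tests are taken when is set by the footnotes to protocol Table 5.2.3: 1:

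- Set A: "Parameters of Set A will be determined at the screening examination"
- Set B: "Parameters of Set B will be determined during treatment periods at the time points given in the" Flow Chart
- Set C: "Parameters of Set C will be determined at the end of trial examination"

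The coagulation tests aPTT and prothrombin time are in Sets A and C but not in Set B. The Flow Chart also marks a safety laboratory at an "Ambulatory visit" on Days -3 to -1, and the table assigns no set to that visit.

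**The concern.** The two documents state different rules and neither acknowledges the other. If the SAP means the first run-in tablet, baseline is the screening value. If it means the Day 1 dose, baseline for most tests is a value taken after the run-in tablets. Changes from these two baselines answer different questions, because only the first includes the run-in exposure.

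Coagulation makes the difference concrete. These tests are not in Set B, so a literal Day 1 baseline is never scheduled for them and no change could be computed, while the SAP rule always finds a value. On the Day 1 reading, a coagulation change measured from screening could also stand unmarked beside changes in other tests measured from Day -3 to -1. The protocol treats thromboembolism as a known Microgynon risk, and aPTT and prothrombin time are the only coagulation tests repeated after screening. It therefore seemed reasonable to ask for their baseline to be explicit.

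**Working it through.** The plan states no figure to reproduce. The check asks which visit supplies the baseline under each reading, and then how far the choice reaches.

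**Step 1. Which visit supplies the baseline.** ALT stands for the tests in all three sets.

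| Rule and reading | ALT | aPTT, prothrombin time |
|---|---|---|
| SAP, first run-in tablet | Screening | Screening |
| SAP, Day 1 dose; Day -3 to -1 visit uses Set B | Day -3 to -1, or Day 1 pre-dose if sampled | Screening |
| SAP, Day 1 dose; that visit uses Set A or C | Day -3 to -1, or Day 1 pre-dose if sampled | Day -3 to -1 |
| SAP, first BI 409306 dose (Day 18) | Day 18 pre-dose | Screening, or Day -3 to -1 if that visit uses Set A or C |
| Protocol, sample on Day 1 itself | Day 1 if sampled, otherwise none | None |
| Protocol, Day 1 taken as the visit just before it | Day -3 to -1 (or Day 1 if sampled) | Day -3 to -1 if Set A or C, none if Set B |

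The SAP rule yields a baseline in every row. The protocol rule can fail, and for coagulation it fails whenever it is read literally. The two rules do not always differ for coagulation: they agree if the protocol's Day 1 means the preceding visit, that visit includes coagulation, and the SAP means the Day 1 dose.

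**Step 2. Is there a Day 1 laboratory sample?** As extracted, the only Day 1 mark in the safety-laboratory column carries footnote 7, which concerns PK samples taken before dosing. Day 19 shows a mark with the same footnote in that column, so the columns may have shifted. If Day 1 has no safety laboratory, the literal protocol baseline is missing for every test, and coagulation is not a special case.

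**Step 3. Which dose does the SAP mean?** For laboratory values and vital signs, SAP 6.1 ends the screening phase at the first administration of study drug and starts the Microgynon phase at the first Microgynon intake. Protocol 7.3.3 assigns measurements before the first intake of trial medication to screening. Protocol 3.3.4.1 places the first administration of trial medication in the run-in. Together these favour the first row of the table, where all tests share the screening baseline and no mixing occurs.

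**Step 4. What the choice changes.** There is no Day 0.

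- Tablets from baseline to end of trial. Run-in: Day -28 to -8 = 21, or Day -49 to -8 = 42. Treatment period: Day 1 to 21 = 21. From screening: 21 + 21 = 42 to 42 + 21 = 63. From Day 1: 21.
- Days to end of trial (Day 33 to 35). From screening: 29 + 33 - 1 = 61 to 70 + 35 - 1 = 104. From the Day -3 to -1 visit: 1 + 33 - 1 = 33 to 3 + 35 - 1 = 37. From Day 1: 33 - 1 = 32 to 35 - 1 = 34.

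These figures measure what a change spans. They do not show any shift in a laboratory result.

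**Step 5. Does the late coagulation value enter the change table?** The only scheduled coagulation value after dosing has finished is at end of trial. The Microgynon residual effect period ends on Day 21 + 10 = Day 31, before that visit. The last BI 409306 dose is on Day 29, so the visit comes 33 - 29 = 4 to 35 - 29 = 6 days later. Whether that counts as on treatment depends on the BI 409306 residual effect period, which is not visible in the public text. If the visit is follow-up, and Days -3 to -1 supplied no coagulation value, these tests have no scheduled on-treatment change under either rule.

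**The case for a change.** The best case for a change is that the protocol fixes a baseline in plain words, the SAP replaces it with another, and SAP Section 4 says nothing has changed. Protocol 7.3.3 leaves the details of phase assignment to the SAP, but its laboratory baseline is stated separately, so the delegation does not cover it. If SAP 6.1 settles the run-in reading, the SAP departs from the protocol for every laboratory test. One sentence would remove the doubt, with no new assessments and no protocol amendment.

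Most of this stands as a point of drafting. The documents disagree, Section 4 is silent, and the set used at the Day -3 to -1 visit is not stated. For vital signs there is only an open wording, since the protocol names no day.

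Three parts do not stand. It is not shown that the tables differ on any reading, because Step 1 contains a case in which the rules agree. Singling out coagulation depends on a Day 1 sample existing for the other tests, which is doubtful. Mixed baselines need the less supported reading of the SAP together with an assumption about the unassigned visit. The request also offers no better rule; it asks only that the rule be written down.

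**Conclusion.** No change follows. This is an editorial mismatch that analysts can resolve sensibly from the rest of the text. Read with its own phase definitions, the SAP takes the screening value as baseline for all laboratory tests. That is a sound choice, because Microgynon is a trial product and the run-in is exposure to it. The protocol's Day 1 wording is the weaker of the two rules, since it may not be executable for any test.

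The reach is small: descriptive laboratory change and reference-range tables for a planned 16 healthy subjects. Comparison with reference ranges, the listings of individual values and the reporting of clinically relevant findings as adverse events all work without a baseline. No PK endpoint, model or confidence interval is touched.

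The conclusion assumes the run-in reading of SAP 6.7. If the Day 1 dose was meant, most tests take the Day -3 to -1 value and coagulation may fall back to screening. The tables remain computable and descriptive, and how far the coagulation change is affected cannot be settled from the public text.

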7. PLANNED ANALYSIS

In general, a set of descriptive statistics to be displayed for continuous variables in the clinical trial report will be as follows:

Non-pharmacokinetic variables:

For End-Of-Text tables, the set of summary statistics is: N, mean, standard deviation (SD), min, median, and max.

Tabulation of frequencies for categorical or categorised data will include all possible categories and display number of observations (subjects) with the percentage relative to the respective treatment sequence / regimen. Percentages will be rounded to one decimal place. The category missing will be displayed if and only if there are actually missing values. Percentages will be based on all subjects in the respective subject set whether they have non-missing values or not.

Pharmacokinetic variables:

The analysis of standard PK parameters will be performed according to [\(4\)](#).

Safety analysis (refer to Section 7.8) will be presented in Sections 15.1 to 15.4 of the CTR and in Appendices 16.2 and 16.1.9.2.

Inferential statistical analyses of PK endpoints (refer to Section 7.5.2) will be presented in Section 15.5 of the CTR and in Appendix 16.1.9.3.

Descriptive data analysis of PK endpoints will be performed by BI and will be presented in Section 15.6 of the CTR.

The format of the listings and tables will follow the standards defined in the BI corporate guideline “Reporting of clinical trials and project summaries” [001-MCG-159] [\(6\)](#) with the exception of those generated for PK calculations.

The individual values of all subjects will be listed, sorted by treatment sequence, subject number, visit and actual treatment (if appropriate). The listings will be included in Appendix 16.2 of the CTR.

For end-of-text tables, the set of summary statistics for non-PK parameters is:

N	number non-missing observations
Mean	arithmetic mean
SD	standard deviation
Min	minimum
Median	median
Max	maximum

For analyte concentrations as well as for all PK parameters, the following descriptive statistics will additionally be calculated:

CV	arithmetic coefficient of variation
gMean	geometric mean
gCV	geometric coefficient of variation

For PK parameters, P10, P90, Q1 and Q3 will be calculated.

The data format for descriptive statistics of concentrations will be identical with the data format of the respective concentrations. The descriptive statistics of PK parameters will be calculated using the individual values with the number of decimal places as provided by the evaluation program. Then the individual values as well as the descriptive statistics will be reported with three significant digits in the CTR.

Tabulations of frequencies for categorical data will include all possible categories and will display the number of observations in a category, as well as the percentage (%) for each treatment group. Percentages will be rounded to one decimal place and will be based on all subjects in the respective subject set whether they have non-missing values or not. The category 'missing' will be displayed only if there are actually missing values.

Units of variables should be given in the titles or column/row descriptors in square brackets (e.g. [mg]).

Exclusion of PK parameters

The ADS ADPP contains column variables APEXC and APEXCO indicating inclusion/exclusion (APEXC) of a PK parameter and an analysis flag comment (APEXCO). All analyses based on the PKS will include parameters if they are not flagged for exclusion; that is APEXC is equal to "Included".

Exclusion of PK concentrations

The ADS ADPC (PK concentrations per time-point or per time-interval) contains column variables ACEXC or ACEXCO indicating inclusion/exclusion (ACEXC) of a concentration and an analysis flag comment (ACEXCO). Exclusion of a concentration depends on the analysis flag comment ACEXCO. For example, if ACEXCO is set to 'ALL CALC', the value will be excluded for all types of analyses based on concentrations. If ACEXCO is set to 'DESC STATS' the value will be excluded from descriptive evaluations per planned time point/time interval. If ACEXCO contains the addition 'TIME VIOLATION' or 'TIME DEVIATION' the value can be used for further analyses based on actual times. If ACEXCO is set to 'HALF LIFE' the value will be excluded from half-life calculation only; the value is included for all other analyses.

Further details are given in 001-MCS-36-472_RD-01 "Noncompartmental Pharmacokinetic / Pharmacodynamic Analyses of Clinical Studies" (4) and 001-MCS-36-472_RD-03 "Description of Analytical Transfer Files and PK/PD Data Files" [\(7\)](#).

